On Day 4, the intervention and control group participants will not receive any lorcaserin/placebo, but will undergo assessments (identical to Day 2).

4-a-6) Measurements

Participants will be monitored to ensure safety of lorcaserin/placebo administration. This monitoring will include a daily review of interim history (via chart review), medications, and laboratory values (details below), as well as assessment for changes in mental status and monitoring for serotonin syndrome (see table 3).

We also will obtain a battery of outcome measures to test the efficacy in improving muscle strength and assess the safety of lorcaserin, as described in tables 3.

All monitoring will be done by assessors blinded to group allocation.

Table 3: Safety and Efficacy Measures (numbers indicate the number of times within each study day that each measurement is performed)

Measurement	Number of assessments			
	Day 1*	Day 2†	Day 3***‡	Day 4†
Safety Measures				
Chart Review	1	1	1	1
Laboratory Tests (details below)	1	1	1	1
EKG	2	1	1	1
RASS sedation score	2***	1	2***	1
CAM-ICU delirium screen	2***	1	2***	1
Neuro Psychiatric Screen	2	1	1	1
Hunter Serotonin Toxicity Criteria	1	1	1	1

Efficacy Measures				
Handgrip Strength (Primary Outcome)	2***	1	2***	1
Arm & leg strength (MMT using MRC Scale)	2***	1	2***	1
Quadriceps Strength using handheld dynamometry	2***	1	2***	1
Lorcaserin serum drug levels [‡]	1	1	1	1
Electromyography & Nerve Conduction Study	once only to assess for any peripheral neuromyopathy****			

MMT: Manual muscle strength testing; MRC: Medical Research Council; HHD: Hand-Held Dynamometry; EKG: Electrocardiogram; RASS: Richmond Agitation Sedation Scale; NPI-C: Neuropsychiatric Inventory - Clinician Rating Scale; CAM-ICU: Confusion Assessment Method for the ICU; Hunter Criteria: will be used to evaluate patients for serotonin syndrome (24)

* 10 mg of lorcaserin or placebo administered

** 30 mg of lorcaserin or placebo administered

*** measures are performed as close to the time as drug or placebo administration as possible (within 4 hours) and as soon as possible (between 2 - 6 hours) after drug or placebo administration, on Days 1 and 3 only

**** EMG & NCS will be performed at any time point after the patient is randomized into study, and will be used to help interpret the results of strength tests

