11. Unable to receive, or unlikely to absorb, study drug (e.g. bowel obstruction, ischemia, or infarction; short gut syndrome)
12. Body mass index $>$ 40
13. Patient not expected to survive $>$ 4 days
14. Pregnancy (based on urine or blood test results based on standard practice in the subject's ICU) or lactation
15. Allergy to lorcaserin or lorcaserin taken in the prior 7 days
16. Enrolled in another interventional drug or physical rehabilitation trial
17. Physician declines for patient to be enrolled
18. Patient or proxy declines consent
19. Unable to reach proxy for consent
20. Non-English speaking

6) Drugs/ Substances/ Devices

6-a) The rationale for choosing the drug and dose or for choosing the device to be used.

It is known that activation of serotonin receptors (5-HT_{2C}) in the spinal cord increases persistent inward sodium current to allow motor neurons to fire repetitively, and lorcaserin, as a selective 5-HT_{2C} agonist was used successfully in rat models (see Background, section 3-d)

The lorcaserin dose that normalizes motor neuron firing in rats is 3 mg/kg. The human dose for weight loss is 10 mg PO twice daily, but doses up to 60 mg were tolerated in clinical trials. Based on rat-to-human allometric scaling of both pharmacokinetic parameters and 5-HT_{2C} receptor sensitivity (EC₅₀), the 3 mg/kg dose in a rat is

Date: 1 August 2016

Principal Investigator: [name] PhD

Application Number: IRB00072940

0.26 mg/kg or 18 mg in a 70 kg adult. Based on doses of lorcaserin that were given to patients prior to FDA approval and rat to human allometric scaling, it appears that treatment of patients with effective doses of lorcaserin is feasible (See Background, section 3-e)

6-b) Justification and safety information if FDA approved drugs will be administered for non-FDA approved indications or if doses or routes of administration or participant populations are changed.

See attached IND Exemption document

6-c) Justification and safety information if non-FDA approved drugs without an IND will be administered.

Not Applicable

7) Study Statistics

7-a) Primary outcome variable.

The primary analysis will compare the mean change in hand grip strength from baseline to post-drug testing across the 30 mg intervention dose vs. control group using a two-sample t-test.

7-b) Secondary outcome variables.

Secondary analyses will include the following:

- 1) replication of the primary analysis for the 10 mg intervention dose vs. control group,

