- 2) replication of the primary analysis excluding any patients with neuropathy based on nerve conduction studies (29) within the intervention group,
- 3) comparison of the change from baseline to post-drug testing across the 10 mg versus 30 mg conditions using a paired t-test
- 4) a PK-PD analysis for all concentration-strength measures for all observations (across the 4 days) using a traditional Emax model pooling all subjects and all time points.

7-c) Statistical plan including sample size justification and interim data analysis.

The sample size (N=10 for lorcaserin and N=5 for placebo) is a convenience sample to establish preliminary data for a potential larger future study. With $\alpha = 0.05$, power = 80%, and a mean (standard deviation) baseline value of 9 (9) kg for the primary outcome of grip strength, under a 30 mg dose of lorcaserin we could detect a difference of >9 kg for the change in strength from baseline to post-drug testing (on the same day) for the intervention group versus no change for the placebo group. This difference represents a 100% increase in strength versus a 400% increase detected with an equivalent dose in the rat model. This calculation assumes that the baseline and post-drug testing measures would be highly correlated ($r = 0.8$). Under a worst case scenario (i.e., no correlation between baseline and post-drug testing), we could detect at least a 220% increase in strength which is adequate given the large increase expected based on rat models.

7-d) Early stopping rules

There are no early stopping rules for this pilot trial.

8) Risks

8-a). Medical risks, listing all procedures, their major and minor risks and expected frequency.

1) Side effects of Drug / Placebo:

Participants will be closely monitored for any side effects related to administration of the study drug or placebo.

The placebo has no known side effects.

Date: 1 August 2016

Principal Investigator: [name] PhD

Application Number: IRB00072940

The study drug, lorcaserin, has been extensively studied, has an excellent safety profile and is FDA approved for chronic use for purposes of weight loss(19). The major potential side-effects are listed below. A full list of side effects is available in Appendix C, the FDA prescribing information.

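### The 80% power figures in section 7-c do not fit the t-test named in 7-a, which has about 76% and 75% power if alpha is two-sided; separately, ANCOVA would give partial protection if the correlation is below 0.8

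*Combined protocol and SAP*

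**What the plan says.** Section 7-a compares mean change in grip strength "across the 30 mg intervention dose vs. control group using a two-sample t-test". It does not say whether the variance is pooled or Welch.

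Section 7-c sets 10 lorcaserin and 5 placebo patients and says this number "is a convenience sample to establish preliminary data for a potential larger future study". It then quotes power, using alpha 0.05 without sidedness, 80% power and "a mean (standard deviation) baseline value of 9 (9) kg for the primary outcome of grip strength". No post-dose SD is given.

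- At r = 0.8: "we could detect a difference of >9 kg for the change in strength from baseline to post-drug testing (on the same day"), against no change on placebo. The next sentence fixes the size: "This difference represents a 100% increase in strength versus a 400% increase detected with an equivalent dose in the rat model". With a baseline mean of 9 kg, 100% is 9 kg.
- In the worst case: "no correlation between baseline and post-drug testing), we could detect at least a 220% increase in strength". That is 2.2 × 9 = 19.8 kg, and the section judges it adequate.

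Table 3 (section 4-a-6) schedules grip strength twice on Day 3. Its footnote places the first test near dosing ("measures are performed as close to the time as drug or placebo administration as possible (within 4 hours") and the second 2 to 6 hours after. A same-day pre-dose value is therefore already collected. The primary analysis subtracts it but does not use it as a covariate.

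**The concern.** With 15 patients, the choice between normal and t quantiles matters. The two-sided 5% critical value is 2.160 on 13 degrees of freedom, against 1.960 for the normal. The printed thresholds look like the normal ones, so a reader would credit the planned test with power that it lacks under the usual two-sided alpha. Section 7-c uses the second threshold to call the design adequate even with no correlation.

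A second, separate point is that the precision of a change score depends on r. The value 0.8 is an assumption, and the plan has no analysis that is less exposed if r turns out lower.

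**Working it through.** **Inputs.** From 7-c: n = 10 and 5, alpha 0.05, power 80%, baseline mean 9 kg and SD 9 kg, r = 0.8 or 0. From 7-a: a two-sample t-test on change, hence 10 + 5 − 2 = 13 df. Assumed because not stated: two-sided alpha, pooled variance and a post-dose SD of 9 kg.

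**Standard errors.** SD of change = 9 × √(2(1 − r)). SE = SD × √(1/10 + 1/5) = SD × 0.5477.

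- r = 0.8: SD 5.69 kg, SE 3.12 kg.
- r = 0: SD 12.73 kg, SE 6.97 kg.

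**Reproducing the plan's figures.** With two-sided normal quantiles, the detectable effect is (1.960 + 0.842) × SE. This gives 8.73 kg (97%) and 19.53 kg (217%), which round to the printed 100% and 220%. The other readings at 10:5 do not fit:

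| Method, 10 vs 5 | 80% effect, r = 0.8 | 80% effect, r = 0 |
|---|---|---|
| Printed in 7-c | 9 kg (100%) | 19.8 kg (220%) |
| Normal, two-sided | 8.73 kg (97%) | 19.53 kg (217%) |
| Normal, one-sided | 7.75 kg (86%) | 17.33 kg (193%) |
| t, 13 df, two-sided | 9.45 kg (105%) | 21.13 kg (235%) |
| t, 13 df, one-sided | 8.19 kg (91%) | 18.31 kg (203%) |

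**Power of the named test at the printed effects** (noncentral t, noncentrality = effect / SE):

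- 9 kg, r = 0.8: noncentrality 2.89, power 76.1%.
- 19.8 kg, r = 0: noncentrality 2.84, power 74.7%.
- Over the unstated choices: one-sided pooled 86.1% and 85.2%; two-sided Welch, by simulation, about 71% and 69%.
- At the 400% rat effect (36 kg) with r = 0: 99.7%.

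**ANCOVA against the change score.** Residual SD is 9 × √(1 − r²) on 12 df. The variance is inflated by 1 + F(1,13)/13 for chance baseline imbalance, and power is averaged over F. Simulation agreed.

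| Effect and r | Change-score t-test | ANCOVA |
|---|---|---|
| 9 kg, r = 0.8 | 76.1% | 76.5% |
| 9 kg, r = 0.7 | 58.8% | 61.8% |
| 9 kg, r = 0.5 | 39.4% | 46.3% |
| 19.8 kg, r = 0 | 74.7% | 94.0% |

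At r = 0, the effect detectable with 80% power is 15.7 kg (174%) with ANCOVA, against 21.1 kg (235%) with the t-test. Break-even is at r of about 0.815. Above that ANCOVA loses a little: where the t-test has 80%, ANCOVA has 79.3% at r = 0.85, 78.2% at 0.90 and 77.2% at 0.95.

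**The case against.** - **The shortfall is conditional.** With one-sided alpha the printed effects would be conservative. This stands, and it is why sidedness must be stated. One-sided alpha still does not reproduce the printed pair.
- **The cause is inferred.** Section 7-c gives no formula, and a two-sided t-test on 15 patients split 8:7 also gives 99% and 222%. This stands as to cause. The trial is randomised 2:1 with 10 and 5 patients, so on either explanation the figures do not describe the two-sided test at the stated allocation.
- **The wording is loose.** More than 9 kg and at least 220% do not strictly exclude 9.45 kg and 235%. But 7-c equates the difference with a 100% increase and presents both figures with 80% power.
- **The gap is smaller than the uncertainty in the inputs.** The t-test reaches 80% at 9 kg if r is 0.819, or if the post-dose SD is 7 kg (80.2%). At a post-dose SD of 10 kg it has 70.5%. This stands, and the post-dose SD should be stated too.
- **No decision turns on it.** The sample size is one of convenience, and a larger study would plan from the observed data. Largely true, and it limits the weight of the point. It does not make the quoted power correct.
- **ANCOVA is a preference.** A change-score t-test is valid in a randomised trial, 7-c already discloses an r = 0 case, and ANCOVA does not restore 80% power at 9 kg when r is below 0.8. All true, which is why it is offered only as an optional improvement.

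**Conclusion.** The concern holds. If alpha is two-sided, variance pooled and the SD 9 kg at both times, the test named in 7-a falls about 4 to 5 points short of the quoted 80%. The effects that it detects with 80% power are about 5 percentage points larger than printed at r = 0.8 and 15 points larger at r = 0. The arithmetic is certain under those assumptions; the use of normal quantiles is an inference from the match. The error is modest and does not call for more patients.

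The ANCOVA point is separate. Its gain is negligible at the planned r = 0.8, a few points at r = 0.7 to 0.5, and large only in the plan's own r = 0 case.

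**What to change.** **(a) Section 7-c.** State the sidedness of alpha, the variance form of the t-test and the assumed post-dose SD. If these are two-sided, pooled and 9 kg, give the effects detectable with 80% power as about 9.5 kg (105%) at r = 0.8 and 21.1 kg (235%) at r = 0. The cost is wording and slightly less favourable figures. The sample size is unchanged.

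**(b) Section 7-a, optional.** Analyse Day 3 post-dose grip by ANCOVA with Day 3 pre-dose grip as covariate. Report the adjusted difference with its 95% CI and keep the change-score t-test as a sensitivity analysis. Fix the choice before unblinding, not from the observed r. Describe it as protection against r below 0.8, not as a repair of the shortfall at 0.8. The cost is one residual degree of freedom (13 to 12) and about 1 to 3 points of power if r is 0.85 to 0.95. No extra patients, visits or data are needed.

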It was recently discovered that patients recovering from sepsis/critical illness have great difficulty recruiting motor units to generate muscle force. Prior to this discovery, the primary etiology of muscle weakness in these patients was thought to be muscle disease (myopathy) and degeneration of peripheral nerve (neuropathy). However, since motor units are composed of a group of muscle fibers contacted by a single motor neuron arising from the spinal cord, these new findings suggested a problem within the spinal cord as the primary cause of weakness in affected patients. Consistent with these clinical findings in critically ill patients, there is a profound deficit in the excitability of motor neurons in the spinal cord of septic rats. Studies characterizing the impaired excitability in rat motor neurons point to a specific deficit in a slowly inactivating type of sodium current (i.e., the persistent sodium current). This type of sodium current has been well characterized in motor neurons; it is known that activation of a subtype of serotonin receptors (5-HT_{2C}) increases this current. In an attempt to normalize motor neuron firing, in prior research septic rats were treated with lorcaserin (a drug approved by the FDA as Belviq® for weight loss via activation of 5-HT_{2C} receptors) and found that motor neuron excitability was normalized such that muscle force production improved 4-fold. The dramatic improvement in strength in rats raises the possibility that lorcaserin might benefit critically ill patients with muscle weakness after sepsis. In this proposal, we propose the first step in translating these findings to patients with intensive care unit (ICU)-acquired weakness. Specifically, we will examine the efficacy and safety of lorcaserin in weak critically ill patients recovering from sepsis. We will assess muscle strength after two escalating doses of lorcaserin in these patients.

2) Objectives

(Include all primary and secondary objectives)

2-1) Evaluate the safety of lorcaserin in intensive care unit (ICU) patients recovering from sepsis.

While lorcaserin is safe for prolonged use for weight loss, it has not been used in ICU patients.

2-2) Compare the effect of lorcaserin vs. placebo on muscle strength in ICU patients recovering from sepsis.

3) Background

(Briefly describe pre-clinical and clinical data, current experience with procedures, drug or device, and any other relevant information to justify the research)

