All participants, clinical staff, and research staff (including those performing outcomes assessments and administering the drug/placebo) will be blinded to the randomization allocation. The investigational pharmacy (which will not be blinded) will prepare the lorcaserin/placebo for administration in similar forms and packaging to prevent unblinding.

If any unexpected, adverse event occurs that may be directly related to the study protocol, unblinding of treatment allocation for that specific participant will occur, as needed, for the principal investigator and IRB (the outcomes assessor(s) would still remain blinded if the patient continued in the trial). Time points and the number of 'unblinding' episodes will be recorded.

4-d) Justification of why participants will not receive routine care or will have current therapy stopped.

All participants, regardless of study group, will continue to receive routine medical care in the ICU. For safety reasons, in consultation with a panel of experts (Drs. [name] – Critical Care; [name] – Clinical Pharmacology; [name] – Psychiatry, [name] – MICU Pharmacist), the following procedures were developed and will be followed in the event a participant is scheduled to receive pharmacologic therapies that may potentially interact with the study drug (see Appendices A and B for list of drugs) to minimize the risk of serotonin syndrome or other potential adverse drug effect from CYP2D6 effect on drug metabolism.

1. First, a non-interacting substitute will be sought in consultation with the primary clinical team.
2. In the event that no safe and effective substitute is available, and the interacting agent is classified in
 - a. Appendix A, participants will be excluded or withdrawn from the study.
 - b. Appendix B participants will not receive more than one other serotonergic agent during the trial, with consideration of the following strategies when/if feasible
 - i. In consultation with the participant's clinical team, a decision will be made regarding the safety of temporarily discontinuing a non-essential drug therapy before the start of the 4-day protocol, and restarting the drug at least 2 days (i.e., 4 half-lives of lorcaserin) after the last administration of lorcaserin/placebo.

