a) Serotonin Syndrome or Neuroleptic Malignant Syndrome (NMS) like Reactions: Although lorcaserin has not been associated with any known cases of either serotonin syndrome or NMS, the safety of co-administration of lorcaserin with other serotonergic or anti-dopaminergic agents has not been established.

b) Cardiac valvular and conduction abnormalities: Asymptomatic aortic or mitral regurgitations were seen in patients who were in a randomized control trial of lorcaserin vs placebo for a one-year period, likely due to long-term activation of serotonin receptors on cardiac interstitial cells. In a similar year-long trial of lorcaserin vs placebo, some patients experienced a decrease in their heart rate over time.

c) Cognitive Impairment and Depression or suicidal thoughts: in trials of at least 1 year duration, lorcaserin administration was associated with difficulty with concentration and attention, difficulty with memory and confusion, and some mood problems such as depression.

d) Psychiatric Disorders (including euphoria and dissociation): have been associated with short-term studies of lorcaserin at supratherapeutic dosages.

e) Hypoglycemia was observed in some participants with Type 2 Diabetes on lorcaserin while concomitantly on a sulfonylurea.

f) Priapism: Although lorcaserin has not been associated with cases of priapism, serotonergic drugs like lorcaserin have been associated with priapism.

2) Risk of stopping/adjusting other medications: There may be risks associated with the temporary stopping of other medications

3) EMG and Nerve Conduction Studies: Participants may experience some discomfort. There might also be some bruising in the area where the wire is inserted. Most subjects will not experience any bleeding with the needle studies; even for patients receiving therapeutic anticoagulation, the reported risk of clinically silent hematoma formation is less than 2% (30). If bleeding occurs, no more than a few drops is expected. The risk of infection is extremely small.

4) Blood sampling: Participants may experience discomfort, bruising or bleeding at the site of blood draws. All patients will have blood drawn for research purposes either through indwelling catheters or percutaneously by either a licensed clinical staff or trained research personnel. Risks of percutaneous blood draws are uncommon and include bleeding, discomfort and bruising.

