The primary investigator ([name]) is a board-certificated critical care physician practicing in the intensive care unit at Johns Hopkins. He will be involved in the daily conduct of the clinical trial and closely supervise the daily screening for patient eligibility, informed consent, and study procedures such outcomes assessments and safety monitoring during the trial. Consequently, immediate knowledge of any unanticipated problem or study deviation that may arise will be available to the P.I. ([name]) on a timely basis for immediate action and reporting to the IRB as necessary. If [name] is unavailable, the study will maintain a list of clinicians associated with the study and [name] research group who can provide medical guidance.

Administration of lorcaserin/Placebo will be done by licensed clinical staff in coordination with the research pharmacy.

Examples of events that are anticipated in this population of critically ill patients include: transient hypoxemia and hypotension, agitation, delirium, skin breakdown, nosocomial infections, glucose dysregulation, deep venous thrombosis/pulmonary embolus, tube feeding intolerance, cardiovascular compromise, end organ compromise or failure (e.g. renal failure) and death. These events and other similar events, which are often the focus of prevention efforts as part of routine ICU care, will not be considered reportable adverse events unless they are considered by [name] to be associated with the study protocol. Serious adverse events are defined any untoward clinical events that are:

- Fatal or immediately life threatening
- Permanently disabling or severely incapacitating
- Requires prolonged inpatient hospitalization
- Important medical events that may not result in death, be life threatening, or require prolonged hospitalization may be considered serious adverse events when, based on appropriate medical judgment, they may jeopardize the patient and may require medical or surgical intervention to prevent one of the serious outcomes listed above.

If clinically important, unanticipated adverse problems or clinically important study-related, serious adverse events occur, they will be recorded on a designated case report form. All events that are serious and unanticipated, or study-related and adverse will be reported to Institutional Review Board within the required reporting timeline.

8-c) Legal risks such as the risks that would be associated with breach of confidentiality.

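### The adverse-event form takes an anticipated ICU event only if it is judged study-related, so events outside the scheduled safety measures have no stated place in the safety data

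*Combined protocol and SAP*

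**What the plan says.** Objective 2-1 is to "Evaluate the safety of lorcaserin in intensive care unit (ICU) patients recovering from sepsis", and the protocol notes that the drug has no prior use in ICU patients. Section 3-f says that adverse events will be observed at set intervals after each dose.

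Section 8-c (plan for reporting unanticipated problems or study deviations) gives examples of events anticipated in this population. They begin with "transient hypoxemia and hypotension, agitation, delirium, skin breakdown, nosocomial infections, glucose dysregulation" and go on to venous thrombosis or embolism, feeding intolerance, cardiovascular compromise, organ failure and death. These and similar events "will not be considered reportable adverse events unless they are considered by" the investigator to be associated with the protocol. Later in the section comes the rule for the form: "If clinically important, unanticipated adverse problems or clinically important study-related, serious adverse events occur, they will be recorded on a designated case report form". A separate sentence then covers what goes to the IRB.

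Section 4-a-6 says of the scheduled measures: "We also will obtain a battery of outcome measures to test the efficacy in improving muscle strength and assess the safety of lorcaserin". Table 3 places chart review, laboratory tests, EKG, RASS, CAM-ICU, a neuropsychiatric screen and the Hunter criteria on each of the four study days, done by blinded assessors. Table 2 adds SOFA on Days 1 and 3. Section 7 contains no safety endpoint and no tabulation of adverse events.

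**The concern.** When background rates are high, a single episode of hypotension or infection can rarely be attributed to a drug. What a small placebo-controlled trial can offer is a count per arm, collected in the same way in both. A form that takes such an event only after a causality judgement gives up that count.

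Some anticipated events also resemble risks that section 8-a lists for the drug. Examples are "difficulty with memory and confusion, and some mood problems such as depression" and a fall in heart rate. At stake is whether the trial's event data can answer objective 2-1 and inform the repeat-dosing work foreseen in section 9-a.

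**Working it through.** The plan states no figure on this point, so the check is mainly one of text.

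**Step 1: routes onto the event form (8-c).** Route A is a clinically important unanticipated problem; an anticipated event fails this by definition. Route B is a clinically important, study-related, serious event; an anticipated event must meet all three conditions. An anticipated event that is attributed but not serious goes to the IRB under the next sentence, yet the form sentence does not name it. A death judged unrelated meets neither route. No other section gives a recording rule for adverse events. The IRB sentence stands apart from the form sentence, so the latter concerns recording and not just reporting.

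**Step 2: what is captured anyway.** The metabolic panel is taken to include glucose and creatinine.

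| Anticipated event | Scheduled capture regardless of attribution |
|---|---|
| Agitation | RASS and neuropsychiatric screen, Days 1-4 |
| Delirium | CAM-ICU, Days 1-4, twice on dosing days |
| Glucose dysregulation | Laboratory panel, once each study day |
| Organ failure | Laboratory panel; SOFA on Days 1 and 3 |
| Cardiovascular compromise | EKG for rate, QT and AV block; SOFA |
| Hypotension, hypoxemia | Chart review; at most indirectly SOFA |
| Skin breakdown, infection, thrombosis, feeding intolerance, death | Chart review only |

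Section 4-a-6.1 gives the purpose of the chart review as safety monitoring and continued eligibility. It has no event list and no rule for what is written down. Timing limits the other rows. On Day 3, Table 3 has one EKG and one laboratory assessment, and 4-a-6.2 and 4-a-6.3 require both before dosing. If those are the only ones, the next fall on Day 4. Table 3 also allows gap days between Days 2 and 3.

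**Step 3: illustration with assumed rates.** Let p be the proportion of patients with an event of one type and q the probability that it passes the filter. Expected recorded counts are 10·p·q on lorcaserin and 5·p·q on placebo. The chance of recording none on lorcaserin is (1 - p·q)^10. With p = 40% and 20%:

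| q | Lorcaserin count | Placebo count | Chance of none on lorcaserin |
|---|---|---|---|
| 1 | 4.0 | 1.0 | 0.6^10 = 0.6% |
| 0.5 | 2.0 | 0.5 | 0.8^10 = 11% |
| 0.25 | 1.0 | 0.25 | 0.9^10 = 35% |
| 0.1 | 0.4 | 0.1 | 0.96^10 = 66% |

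With p = 60% and 30% and q = 0.2, the counts fall from 6.0 and 1.5 to 1.2 and 0.3, and the chance of none on lorcaserin is (1 - 0.12)^10 = 28%. The expected recorded rates are 0.12 and 0.06, still 2 to 1.

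**Step 4: what a zero would mean.** The exact two-sided 95% upper limit for 0/10 is 1 - 0.025^(1/10) = 30.8%; for 0/5 it is 52.2%. Under filtering, the limit applies to p·q. At q = 0.5 it allows p up to 0.308/0.5 = 62%. At q = 0.25, 0.308/0.25 exceeds 1, so p is not bounded at all.

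**Step 5: power with full recording.** Fisher's exact test at two-sided 5% with 10 and 5 patients has power of about 13% at 60% versus 30%, and about 6% at 40% versus 20%.

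**The case against.** The strongest reply is that safety rests on the scheduled battery and not on the event form. Much of this stands. The measures in Step 2 and the daily Hunter criteria need no causality judgement. Nor do the discontinuation criteria in 4-f, after which data collection continues. AV block, QT prolongation, euphoria, hallucinations, serotonin syndrome and priapism are not on the anticipated list by name. The hypoglycemia in 8-a was seen with sulfonylureas, which are an exclusion, and the cognitive effects came from trials of at least a year. It is also fair that the filter sentence says reportable, not recorded, and that the form sentence does not contain the word only. The restriction is an inference from the sole recording rule given.

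A reader might infer four stronger things that the documents do not support:

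- That the rule deletes a between-arm difference. Uniform attribution thins both arms and leaves the expected ratio unchanged, as Step 3 shows.
- That organ failure and glucose changes escape every scheduled measure. Laboratory tests and SOFA cover them in part.
- That attribution is biased by code breaks. Under 4-c, "unblinding of treatment allocation for that specific participant will occur, as needed, for the principal investigator and IRB", but this follows an unexpected, possibly related event, and attribution is otherwise made blind. What remains is a later event in a participant already unblinded.
- That a planned safety comparison is damaged. Objective 2-1 says evaluate, and section 7 plans no such comparison. Section 4-e implies controlled assessment of cognitive and psychological symptoms, but those come from the scheduled instruments.

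**Conclusion.** The narrower point holds. Followed as written, 8-c leaves unattributed deaths, hypotension, hypoxemia, thrombosis, infection, feeding intolerance and between-check events off the event form, and nothing else says where they are recorded. The event data therefore cannot fully support objective 2-1, nor use the placebo arm to judge events with a high background rate. Many drug-plausible effects are still measured in both arms, so the gap is partial.

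The text settles the existence of the gap. Its size is unknown: every event rate and filter probability above is an assumption. Over the filter range of 0.5 to 0.1, with 40% of lorcaserin patients affected, the chance of an empty lorcaserin record runs from 11% to 66%, against 0.6% with full recording. The conclusion also assumes that the form sentence is meant to be complete. If the sponsor already records all events in practice, the protocol only needs to say so.

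**What to change.** In 8-c, state that the attribution and expectedness filter applies to IRB reporting only. Add that every adverse event and serious adverse event found at the daily chart review, from first dose to the end of Day 4, is entered on the case report form in both arms, whatever its expectedness or attribution. The review on Day 3 should look back over any gap days. Enter the blinded causality judgement before any code break for that participant; this changes the order of documentation, not the grounds for unblinding.

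In section 7, add a descriptive summary of events by arm and dose day with exact confidence intervals. Plan no formal comparison, given the power in Step 5.

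The cost is modest extra form entry for 15 patients whose charts are already reviewed on each study day. No added tests or visits are needed.
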